2.2 DISPOSITION OF PATIENTS

This section describes patient disposition for both patient study status and the patient analysis populations.

Screened patients will be defined as any patient who has signed the informed consent form.

Randomized patients consist of all Cohort 3 patients who have had a treatment kit number allocated and recorded in the interactive response technology (IRT) database, regardless of whether the treatment kit was used.

For cohort 3, patients treated without being randomized, if any, will not be considered as randomized and will not be included in any efficacy population.

For patient study status, the total number of patients in each of the following categories will be presented using a summary table:

- Screened patients,
- Screen failure patients and reasons for screen failure (if data is available),
- Treated patients (Stage 1),
- Randomized patients (Stage 2),
- Nonrandomized but treated patients (Stage 2),
- Randomized and treated patients (Stage 2),
- Randomized but not treated patients (Stage 2),
- Number and percentage of patients who completed the treatment epoch for PAP,
- Number and percentage of patients who did not complete the treatment epoch for PAP, with corresponding reasons.
- Patients who continued into ETP,
- Patients who completed ETP,
- Number and percentage of patients who did not complete the ETP treatment, with corresponding reasons,
- Number and percentage of patients who did not complete the ETP follow-up, with corresponding reasons (will be included in final study report only).
- Number and percentage of patients who received increased or decrease dose, i.e. increase from 20 mg/kg qow to 40 mg/kg qow (Cohort 1), or decrease from 40 mg/kg qow to 20 mg/kg qow.

For all categories of patients (except for the screened and randomized/nonrandomized categories), the summaries will be provided by study cohort and randomized treatment, and percentages will be calculated using the number of safety patients (Stage 1) or randomized patients (Stage 2) as the denominator.

A listing of patients who received increased or decrease dose will also be provided.

All critical or major deviations potentially impacting efficacy analyses, randomization (Cohort 3), and drug-dispensing irregularities, and other major or critical deviations will be listed by patient for all enrolled patients and also summarized in tables giving numbers and percentages of deviations by study cohort and randomized treatment.

Additionally, the analysis populations for safety, PK and efficacy ([Section 2.3](#)) will be summarized in a table by number of patients in the randomized population.

2.2.1 Randomization and drug dispensing irregularities

Randomization and drug-dispensing irregularities occur whenever:

- A randomization is not in accordance with the protocol-defined randomization method, such as a) an ineligible patient is randomized, b) a patient is randomized based on an incorrect stratum, c) a patient is randomized twice, or d) in a dynamic randomization scheme the treatment assignment is, in fact, not random, due to a computer program error; OR
- A patient is dispensed an IMP kit not allocated by the protocol-defined randomization, such as a) a patient at any time in the study is dispensed a different treatment kit than as randomized (which may or may not contain the correct-as-randomized IMP), or b) a nonrandomized patient is treated with IMP reserved for randomized patients.

Randomization and drug-dispensing irregularities will be monitored throughout the study and reviewed on an ongoing basis.

All randomization and drug-dispensing irregularities will be documented in the CSR. Whether any of these constitute a major protocol deviation is deferred to the decision by the clinical team before the DBL. If the number of irregularities is large enough to make a tabular summary useful, the irregularities will be categorized and summarized among randomized patients (number and percentages). Nonrandomized, treated patients will also be described.

Randomization and drug-dispensing irregularities to be prospectively identified include but are not limited to:

Randomization and drug allocation irregularities
Kit dispensation without IRT transaction
Erroneous kit dispensation
Kit not available
Randomization by error
Patient randomized twice
Stratification error
Patient switched to another site
Patient nonrandomized but treated

2.3 ANALYSIS POPULATIONS

2.3.1 Safety population

The safety population is the primary population for Stage 1 and the overall study safety analysis.

The safety population will include patients who receive at least 1 infusion (partial or total). The safety population will be analyzed according to treatment received. For PAP, safety population includes patients who receive at least 1 infusion in PAP. For ETP, safety population includes patients who receive at least 1 infusion in ETP. Overall safety of alglucosidase alfa will be based on patients who receive at least 1 infusion during either PAP or ETP.

For Cohort 1 and Cohort 2, patients for whom it is unclear whether IMP was administered will be included in the safety population. For cohort 3, randomized patients for whom it is unclear whether they took the IMP will be included in the safety population as randomized.

For Cohort 3, nonrandomized but treated patients, if any, will not be part of the safety population in PAP; however, their safety data will be presented separately in PAP.

2.3.2 Efficacy populations

For Cohort 3, patients treated without being randomized, if any, will not be considered randomized and will not be included in any efficacy population.

The modified intent-to-treat (mITT) population is defined as all randomized patients in Cohort 3 who received at least 1 infusion and with evaluable baseline efficacy assessment. Patients will be analyzed in the treatment group to which they are randomized.

The mITT population is the primary population for Cohort 3 (Stage 2) efficacy analysis.

2.3.3 Additional analysis populations

The ETP population will consist of safety patients who receive at least one avalglucosidase alfa dose during ETP.

The PK population will consist of patients from the safety population in PAP who have evaluable drug concentration data. PK analysis for cohort 3 patients who switch to avalglucosidase alfa during the ETP will be reported in the final CSR.

For Cohort 1 and Cohort 2, the PD or pharmacogenetic analysis population for the parameter of interest will consist of safety patients who have evaluable PD or pharmacogenetic data for the parameter of interest. For cohort 3, the PD or pharmacogenetic analysis population for the parameter of interest will consist of mITT patients who have evaluable PD or pharmacogenetic data for the parameter of interest.

The ADA evaluable population will consist of patients from safety population who have at least one ADA sample taken post-baseline after drug administration that is appropriate for ADA testing with a reportable result. Patients with missing or non-reportable baseline samples and reportable post-baseline samples will be considered as evaluable.

2.4 STATISTICAL METHODS

Unless otherwise specified, safety analyses will use the safety population, where patients who receive at least one infusion of avalglucosidase alfa in PAP will be assigned to the avalglucosidase alfa arm for the PAP safety analysis purposes. Efficacy analyses will use the mITT population, where patients will be considered to be in the treatment group to which they were randomized. In addition, efficacy will also be summarized for all cohorts based on the safety population.

In general, all summary statistics will be computed and displayed by study cohort and treatment arm. Summary statistics for continuous variables will minimally include the number of available data (n), mean, standard deviation (SD), minimum, median, and maximum. For categorical variables, n and percentages will be presented and denominators for the percentages will be based on the analysis population used. For categorical variables, frequencies and percentages will be presented. Graphical displays will be provided as appropriate.

2.4.1 Demographics and baseline characteristics

Demographics and baseline characteristics parameters described in [Section 2.1.1](#) and physical examination parameters described in [Section 2.1.3.6](#) will be analyzed by study cohort and treatment arm among patients who received at least one dose of avalglucosidase alfa in either PAP and/or ETP, using summary statistics, based on the safety population and also in the mITT population. Denominators for the percentages will be based on the analysis population used, unless otherwise specified.

Medical history will be summarized by body system and preferred term in the safety population.

Z-scores for weight, height/total body length, BMI and head circumference will be also summarized according to the clinical growth charts of Centers for Disease Control and Prevention for applicable patients (8).

P-values on demographic and baseline characteristic data will not be calculated.

No specific description of the safety or efficacy parameters will be provided at baseline. If relevant, the baseline values will be described along with each safety or efficacy analysis.

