6 STUDY DESIGN

6.1 DESCRIPTION OF THE STUDY

ACT14132 is a multi-stage, phase 2, open-label, multicenter, multinational, ascending dose cohort, repeated intravenous (IV) infusion study of avalglucosidase alfa in pediatric patients with IOPD who have been previously treated with alglucosidase alfa and demonstrated clinical decline (Stage 1) or sub-optimal clinical response (Stage 2) in specified respiratory function, motor skills, cardiac parameters, and/or new onset of ptosis.

Stage 1

- Cohort 1 – at least 5 IOPD patients will receive avalglucosidase alfa at 20 mg/kg qow for 6 months.
- Cohort 2 – at least 5 IOPD patients will receive avalglucosidase alfa at 40 mg/kg qow for 6 months.

Stage 2

- Cohort 3 – at least 10 IOPD patients will be randomized 1:1 to receive avalglucosidase alfa at the highest tolerated avalglucosidase alfa dose in Stage 1 (20 mg/kg qow or 40 mg/kg qow) or alglucosidase alfa treatment at current stable dose (defined by dose of alglucosidase alfa administered regularly for a minimum of 6 months immediately prior to study entry) for 6 months. The randomization will be stratified on gender.

The first 5 patients will be enrolled in the 20 mg/kg qow dose cohort. If determined safe by an independent DMC after the 3rd patient in the 20 mg/kg qow group (Cohort 1) has received the 3rd infusion of avalglucosidase alfa and after 5 patients have started treatment in Cohort 1, the next cohort of avalglucosidase alfa at higher dose (40 mg/kg qow) will be initiated (Cohort 2). Cohort 3 will be initiated after determination of the highest tolerated avalglucosidase alfa dose in Cohort 1 and Cohort 2 after at least 5 patients in Cohort 1 and at least 5 patients in Cohort 2 have received the 7th dose of avalglucosidase alfa (or completed Week 13 with a minimum of 6 infusions).

After completion of treatment for 6 months (Week 25) and data collection for the principal analysis, the patients will continue on long-term avalglucosidase alfa treatment and follow-up in the Extension Period for up to a total of 7 years in the study. Cohort 3 patients receiving alglucosidase alfa will have the option to switch to treatment with avalglucosidase alfa in the extension period or discontinue the study. The data cut-off for the primary analysis will be after the last patient in Cohort 3 has completed 6 months of treatment (Week 25).

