After completion of treatment for 6 months (Week 25) and data collection for the principal analysis, the patients will continue on long-term avalglucosidase alfa treatment and follow-up for up to a total of 7 years in the study.

Cohort 3 patients receiving alglucosidase alfa during the treatment period (Day 1 to Week 25 [Month 6]) will have the option to switch to treatment with avalglucosidase alfa in the extension period or discontinue the study.

8.1.2 Extension period: Week 27 to Week 145 (Month 36) and additional extension period from Week 147 onwards

All patients (from Cohorts 1, 2 and 3) will receive avalglucosidase alfa administered by IV infusion qow starting at V16/W27 continuing up to V76/W145 for a total of up to 60 doses. In order to allow study participants to continue to receive the investigational medicinal product (IMP) after Week 145, the study is extended to an additional period of up to 226 weeks or until avalglucosidase alfa is approved in the patient's country, whichever comes first; (refer to Appendix C [[Section 17.3.1](#)] for definition applicable for UK patients) in which the patients will receive avalglucosidase alfa administered by IV infusion qow for up to an additional 72 doses.

- Participants in Cohort 1 will receive avalglucosidase alfa at a dose of 20 mg/kg qow. If a patient in Cohort 1, receiving 20 mg/kg qow avalglucosidase alfa, experiences further clinical decline at or after Week 25 when compared to prior to enrollment in ACT14132, and as defined by more rapid worsening of criteria of clinical decline, which is sustained on repeated study assessments, the patient may be managed per the discretion of the Investigator, which may include return to treatment with commercially available alglucosidase alfa (and termination of trial participation) or increasing the avalglucosidase alfa dose to 40 mg/kg qow (once this dose is considered acceptable after the end-of-cohort 2 DMC meeting) or MTD (once established) while being enrolled in the extension period of the study.
- Participants in Cohort 2 will receive avalglucosidase alfa at 40 mg/kg qow or MTD (once established).
- Participants in Cohort 3 will receive the MTD of avalglucosidase alfa as determined based on safety data from both dose levels in Cohort 1 and Cohort 2.

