1 OVERVIEW AND INVESTIGATIONAL PLAN

1.1 STUDY DESIGN AND RANDOMIZATION

ACT14132 is a multi-stage phase 2 open-label, multicenter, multinational, ascending dose cohort, repeated intravenous infusion study of avalglucosidase alfa in pediatric patients with infantile-onset Pompe disease (IOPD) who have been previously treated with alglucosidase alfa and demonstrated clinical decline (Stage 1) or sub-optimal clinical response (Stage 2) in specified respiratory function, motor skills, cardiac parameters, and/or presence of ptosis.

Stage 1:

- Cohort 1 – at least 5 IOPD patients will receive avalglucosidase alfa at 20 mg/kg every other week (qow) for 6 months.
- Cohort 2 – at least 5 IOPD patients will receive avalglucosidase alfa at 40 mg/kg qow for 6 months.

Stage 2:

- Cohort 3 – at least 10 IOPD patients will be randomized 1:1 to receive avalglucosidase alfa at the highest tolerated avalglucosidase alfa dose in Stage 1 (20 mg/kg qow or 40 mg/kg qow) or alglucosidase alfa treatment at current stable dose (defined by dose of alglucosidase alfa administered regularly for a minimum of 6 months immediately prior to study entry) for 6 months.

If determined safe by an independent Data Monitoring Committee (DMC) after the 3rd patient in the 20 mg/kg qow group (Cohort 1) has received the 3rd infusion of avalglucosidase alfa, and after 5 patients have started treatment in Cohort 1, the next cohort of avalglucosidase alfa at higher dose (40 mg/kg qow) will be initiated (Cohort 2). Cohort 3 will be initiated after determination of the highest tolerated avalglucosidase alfa dose in Cohort 1 and Cohort 2 after at least 5 patients in Cohort 1 and at least 5 patients in Cohort 2 have received the 7th dose of avalglucosidase alfa (or completed Week 13 with a minimum of 6 infusions).

Upon confirmation by the Investigator or sub-Investigator (if appropriately delegated) that the patient meets all eligibility criteria and completion of the screening and baseline assessments, in Stage 2 of the study (Cohort 3), at least 10 eligible IOPD patients will be randomized 1:1 to receive avalglucosidase alfa at the highest tolerated avalglucosidase alfa dose in Stage 1 or alglucosidase alfa treatment at current stable dose for 6 months (defined by dose of alglucosidase alfa administered regularly for a minimum of 6 months immediately prior to study entry). The randomization will be stratified on gender.

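### SAP 2.4.1 ties the by-arm baseline tables to ever receiving avalglucosidase alfa, so a Cohort 3 control who never switches is missing from those descriptive tables

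*SAP*

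**What the plan says.** SAP 2.4.1 presents demographics, baseline characteristics and physical examination parameters by cohort and treatment arm "among patients who received at least one dose of avalglucosidase alfa in either PAP and/or ETP". PAP is the 25-week primary analysis period and ETP the extension period. The same sentence names the analysis sets: "based on the safety population and also in the mITT population". The next sentence adds: "Denominators for the percentages will be based on the analysis population used", unless stated otherwise.

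The populations themselves carry no such condition. SAP 2.3.2 defines mITT as "all randomized patients in Cohort 3 who received at least 1 infusion and with evaluable baseline efficacy assessment". SAP 2.3.1 asks only for one infusion, partial or complete, without naming a drug.

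Cohort 3 is small: "at least 10 eligible IOPD patients will be randomized 1:1" (SAP 1.1). After Week 25, patients on alglucosidase alfa "will have the option to switch to treatment with avalglucosidase alfa in the extension period or discontinue the study" (Protocol 8.1.1). Protocol 8.1.2 puts the first extension infusion at Week 27. On the timing of the primary analysis, Protocol 6.1 states: "The data cut-off for the primary analysis will be after the last patient in Cohort 3 has completed 6 months of treatment (Week 25". SAP 4 plans the database lock about 30 days after the last PAP visit.

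**The concern.** The exposure condition treats the two randomised arms differently. It is met automatically in the avalglucosidase alfa arm. In the control arm it is met only by patients who complete the treatment period, choose to continue and receive an extension infusion. Membership of the control column in a baseline table would therefore depend on something that happens about six months after randomisation.

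That matters more than usual here. Randomisation is stratified on gender only, with nominally five patients per arm, so chance imbalance in CRIM status, genotype, age at first treatment or ventilator use is quite possible. Chart-review status also feeds the outcome. In SAP Table 1, a domain with suboptimal response or decline at baseline scores 2, 1 or 0, against 1, 0 or -1 without it. The same change category is thus worth one point more. A reader judging whether the arms were comparable needs these characteristics for the patients who were actually tested.

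**Working it through.** The plan gives no figure to reproduce: SAP 1.3 states that no formal sample size calculation was made. The check has three parts.

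**1. Who is in each table.** Take a Cohort 3 control who is randomised, infused with alglucosidase alfa, has an evaluable baseline, and never receives avalglucosidase alfa.

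| Place in the SAP | Patient included? |
|---|---|
| 2.3.1 safety population | Yes, one infusion suffices |
| 2.3.2 mITT population | Yes |
| 2.4.4 PAP safety analyses | Yes, as a patient who received only alglucosidase alfa |
| 2.4.8 composite score test | Yes, it uses mITT |
| 2.4.1 medical history | Yes, unrestricted safety population |
| 2.4.1 demographics and baseline characteristics | No |

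The last row is the odd one out. It also clashes with the denominator rule. If 4 of 5 controls are counted over a denominator of 5, the category percentages add to 4/5 = 80%.

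**2. Timing.** With study day = (week - 1) × 7 + 1:
- Week 25: 24 × 7 + 1 = Day 169, which agrees with SAP Table 5.
- Week 27: 26 × 7 + 1 = Day 183.
- Planned gap: 183 - 169 = 14 days. With ±7 days on each infusion visit, the gap runs from 14 - 14 = 0 to 14 + 14 = 28 days.

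At a cut-off set on the day the last Cohort 3 patient reaches Week 25, a control who reached Week 25 less than about 14 days earlier would have no avalglucosidase alfa dose on record. If the order of entry is random and the split is 5:5, the last patient is a control with probability 5/10 = 50%.

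**3. Size.** With 5 controls and k omitted, the share of the arm lost is k/5 and of Cohort 3 is k/10:
- k = 1: 4 controls shown; 20% of the arm, 10% of Cohort 3.
- k = 2: 3 shown; 40% and 20%.
- k = 3: 2 shown; 60% and 30%.

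The avalglucosidase alfa column stays at 5 throughout.

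The documents give no rate of declining the switch. If each control independently fails to switch with an assumed probability p, the chance that at least one of five is omitted is 1 - (1 - p)^5:

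| Assumed p | 5% | 10% | 20% | 30% |
|---|---|---|---|---|
| At least one omitted | 23% | 41% | 67% | 83% |

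**The case against.** The strongest reply is that this is a drafting conflict with limited reach, and most of that reply stands.

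- **Other baseline data survive.** Laboratory, vital-sign and ECG summaries include baseline by cohort and arm (SAP 2.4.4.3 to 2.4.4.5). Physical examination is summarised again without the condition (2.4.4.6). Efficacy and tertiary endpoints are summarised for all treated patients, and chart-review measurements also enter the changes from pre-study in 2.4.8. What is lost is mainly demographics, Pompe disease history and the tabulated chart-review status.
- **The not-yet-switched case is uncertain.** The cut-off falls after the last Week 25 visit, not necessarily on that day, and lock follows about 30 days later, against a planned 14 days to Week 27. PAP exposure in SAP 2.4.3.1 ends at the first ETP dose for continuing patients, which suggests those dates are expected to be available. No section says so outright.
- **The mITT table might be meant as unrestricted.** The wording does not support this: one sentence applies the condition to both populations.

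A reader might also infer that non-switching controls drop out of the randomised comparison itself. The documents do not support that. SAP 2.4.8 tests the composite in mITT, analysed as randomised and with no exposure condition, and SAP 2.4.4 keeps a group for patients who received only alglucosidase alfa in PAP.

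The reply does not reach the control who never switches: that patient is omitted at any cut-off.

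**Conclusion.** The sentence is wrong as written and should be corrected. It conflicts with the SAP's own safety and mITT definitions and with the denominator rule that follows it, and it makes the control column of a baseline table depend on a later choice.

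The never-switched case is firm. The not-yet-switched case is conditional on which doses are counted between the cut-off and the lock.

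The 20% per patient rests on exactly five controls. Cohort 3 has a minimum of 10 patients, so a larger arm would lose a smaller share per omission. The 23% to 83% range rests entirely on assumed refusal rates. If all controls switch and their doses are counted, nobody is lost. No p-values are planned for baseline data, and no hypothesis test, efficacy estimate or safety endpoint changes.

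**What to change.** In SAP 2.4.1, delete the exposure condition for the PAP baseline tables. State that demographics and baseline characteristics are summarised by cohort and arm for all safety patients (by treatment received) and for all mITT patients (as randomised). Keep the ever-received-avalglucosidase-alfa restriction only for tables describing the overall avalglucosidase alfa pool of SAP 2.4.4, where it fits.

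While editing, check SAP 2.4.2. The prior and concomitant medication summaries carry a similar exposure condition, which in the available text names alglucosidase alfa.

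The cost is one sentence in the SAP and the matching table shells. No data collection, test or estimate is affected.
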